**Table 4: Potential Dose Reduction and Increase Levels for Itacitinib**

Current Dose	First Dose Reduction	Second Dose Reduction
Initial dose for each cohort disclosed in Section 5.2.1	50%	Discontinue

#### 5.6.4. Tapering of Itacitinib

If a subject has achieved CR or VGPR at Day 180, investigators may begin to taper the dose of itacitinib by 1 dose level provided corticosteroids have been discontinued for at least 8 weeks following institutional guidelines. Subsequent tapering may occur within 28 to 56 days after the initial taper as appropriate.

Subjects who are still receiving calcineurin inhibitors or other agents for GVHD prophylaxis at this time may continue to do so at the treating investigator's discretion.

Investigators wishing to initiate a taper of itacitinib at an earlier timepoint may do so upon consultation with approval from the sponsor's medical monitor.

If GVHD signs/symptoms worsen during the taper of itacitinib, the dose may be escalated by 1 dose level. If the subject requires additional systemic therapy (includes restarting of

corticosteroids), then the subject will be considered as having progression of disease and withdrawn from study treatment.

If subjects completely taper off itacitinib and GVHD signs/symptoms reappear at a later time, subjects may enter the re-treatment period at the investigator's discretion. Assessments would be performed as per the re-treatment assessment schedule listed in [Table 5](#).

### **5.6.5. Criteria for Permanent Discontinuation of Itacitinib**

The occurrence of unacceptable toxicity not caused by the underlying disease or malignancy will be presumed to be related to study drug treatment and will require that the study drug be permanently discontinued. Unacceptable toxicity is defined as follows:

- Occurrence of an AE that is related to treatment with the study drug that, in the judgment of the investigator or the sponsor's medical monitor, compromises the subject's ability to continue study-specific procedures or is considered to not be in the subject's best interest.
- Persistent AE requiring a delay of therapy for more than 14 days, unless a greater delay has been approved by the sponsor.

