- Any Grade  $\geq 3$  nonhematologic toxicity that can be reasonably attributed to study treatment.  
Any Grade  $\geq 3$  nonhematologic toxicities that may be related to underlying GVHD (eg, nausea, vomiting, diarrhea, rash) will not be considered as DLTs.
- Any Grade  $\geq 3$  clinical chemistry laboratory abnormalities that are considered clinically significant that can reasonably be attributed to study treatment. Transient ( $\leq 72$  hours) abnormal laboratory values without associated clinically significant signs and symptoms and not leading to hospitalization will not be considered as DLTs.
- Any toxicity that can be reasonably attributed to study treatment and leading to treatment discontinuation for more than 2 weeks.

Subjects will be monitored according to Section [9.8](#).

In all cases, investigators are free to employ any measures or concomitant medications, after discussion with the sponsor, necessary to optimally treat the subject.

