#### **5.6.3. Criteria and Procedures for Dose Interruptions and Modifications of Itacitinib**

If the drugs need to be interrupted due to toxicity, subjects should be evaluated on a weekly basis until resolution/improvement of the AE. Subjects may resume treatment if no medical condition or other circumstance exists that, in the opinion of the investigator, would make the subject unsuitable for further participation in the study. Treatment with itacitinib may be delayed up to 14 days to allow for resolution of toxicity. The investigator should contact the sponsor medical monitor to discuss cases where treatment has been delayed for more than 14 days before restarting treatment.

Because subjects may enter the study with compromised bone marrow function, these dose reductions are provided as guidelines (see [Table 3](#) and [Table 4](#)); individual decisions regarding dose reduction should be made using clinical judgment and an individual benefit/risk assessment, taking into account relatedness of the AE to the study drug and the subject's underlying condition. Adverse events that have a clear alternative explanation or transient ( $\leq 72$  hours) abnormal laboratory values without associated clinically significant signs or symptoms may be exempt from dose-reduction rules.

The starting dose in each cohort may be reduced based on toxicity (ie, approximately 50% of the initial dose in each cohort). The dose might also be modified based on PK data. Subjects who

are unable to tolerate itacitinib at the reduced dose (50% decrease of the initial dose in each cohort) should be withdrawn from study treatment. The sponsor's medical monitor may be consulted for advice.

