**Table 3: Guidelines for Interruption and Restarting of Itacitinib**

ADVERSE EVENT	ACTION TAKEN
Chemistry	

 
AST and/or ALT <math>> 3.0 \times \text{ULN}</math>
 
	
 
Interrupt for up to 14 days until the toxicity has resolved to <math>\leq</math> Grade 1. Exceptions require sponsor approval.
 
Restart at previous dose. If assessed as related to itacitinib, restart at next lower dose and monitor as clinically indicated.
 

 
Total bilirubin elevations that occur in the presence of GVHD response that cannot be attributed to new liver GVHD or concomitant therapy.
 
	
Total bilirubin <math>3.0\text{-}5.0 \times \text{ULN}</math>:
 
 
Reduce dose by 1 level and repeat assessment within 7 days. If elevation persists: 
 
Interrupt until bilirubin <math>\leq 1.5 \times \text{ULN}</math>.
 
Monitor LFTs weekly or more frequently as appropriate.
 
Resume previous dose if resolved in 14 days; if <math>> 14</math> days, maintain reduced dose.
 
 
 
 
Total bilirubin <math>> 5.0\text{-}10.0 \times \text{ULN}</math>:
 
 
Interrupt and repeat assessment within 7 days. If elevation persists: 
 
Keep interruption until bilirubin <math>\leq 1.5 \times \text{ULN}</math>.
 
Monitor LFTs weekly or more frequently as appropriate.
 
Resume previous dose if resolved in 14 days; if <math>> 14</math> days, resume at reduced dose.
 
 
 
 
Total bilirubin <math>> 10.0 \times \text{ULN}</math>:
 
 
Interrupt and repeat assessment within 7 days. If elevation persists: 
 
Keep interruption until bilirubin <math>\leq 1.5 \times \text{ULN}</math>.
 
Monitor LFTs weekly or more frequently as appropriate.
 
Resume at reduced dose if resolved in 14 days; if <math>> 14</math> days, discontinue treatment and monitor as appropriate.
 
 
 

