
 
Total bilirubin elevations that occur in subjects with Stage 1/2 liver GVHD that cannot be attributed to worsening liver GVHD or concomitant therapy.
 
	
Total bilirubin <math>> 3.0 \times \text{ULN}</math>:
 
 
Repeat assessment within 7 days. If elevation persists: 
 
Reduce dose by 1 dose level.
 
Resume previous dose if bilirubin <math>\leq 3.0 \times \text{ULN}</math>.
 
 
 

Hematology	

 
<math>\text{ANC} < 0.5 \times 10^9/\text{L}</math>, suspected as unrelated to study treatment (eg, GVHD, active cytomegalovirus viremia).
 
	
 
Reduce dose by 1 dose level.
 
Monitor ANC count as clinically indicated.
 
Resume previous dose if ANC count is <math>\geq 0.5 \times 10^9/\text{L}</math> for more than 7 days.
 

 
<math>\text{ANC} < 0.5 \times 10^9/\text{L}</math>, suspected as related to study treatment.
 
	
 
Interrupt for up to 14 days.
 
Monitor ANC count as clinically indicated.
 
Resume at a reduced dose if ANC count is <math>\geq 0.5 \times 10^9/\text{L}</math> for more than 7 days. If the subject's ANC count remains at <math>\geq 0.5 \times 10^9/\text{L}</math> for more than 7 days after resuming treatment at a lower dose, the previous dose may be resumed.
 

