**Table 3: Guidelines for Interruption and Restarting of Itacitinib (Continued)**

ADVERSE EVENT	ACTION TAKEN
Hematology (continued)	
• Platelet count is $< 10 \times 10^9/L$ , or platelet count has decreased by $\geq 50\%$ from baseline, suspected as unrelated to study treatment.	
 
• Reduce dose by 1 dose level.
 
• Monitor platelet count as clinically indicated.
 
• Resume at previous dose if platelet count returns to <math>\geq 20 \times 10^9/L</math> for more than 7 days.
 

• Platelet count is $< 10 \times 10^9/L$ , or platelet count has decreased by $\geq 50\%$ from baseline, suspected as related to study treatment.	
 
• Interrupt for up to 14 days.
 
• Monitor platelet count as clinically indicated.
 
• Resume at a reduced dose if platelet count returns spontaneously (without transfusion support) to <math>\geq 20 \times 10^9/L</math> for more than 7 days or within 75% of baseline value. If the subject's platelet count remains at <math>\geq 20 \times 10^9/L</math> without transfusion support for an additional 7 days, the previous dose of study drug may be resumed.
 

Other toxicities	
• Any Grade 1 or Grade 2 toxicity.	
 
• Continue treatment and manage the toxicity.
 
• Monitor as clinically indicated.
 

• Any Grade 3 toxicity, if clinically significant and not manageable by supportive care.	
 
• Interrupt up to 14 days until toxicity resolves to <math>\leq</math> Grade 1.
 
• Restart at same dose; if assessed as related to itacitinib, restart at next lower dose and monitor as clinically indicated.
 

• Any recurrent Grade 3 toxicity at 100 mg QD dose.	
 
• Discontinue study treatment; follow-up per Protocol. Exceptions require sponsor approval.
 

• Any other Grade 4 toxicity.	
 
• Discontinue study treatment; follow-up per Protocol.
 

ALT = alanine aminotransferase; ANC = absolute neutrophil count; AST = aspartate aminotransferase; GVHD = graft-versus-host disease; LFT = liver chemistry test; QD = once daily; ULN = upper limit of normal.

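### Table 3, sections 5.6.3 and 5.6.5 and the DLT definition give incompatible outcomes for itacitinib holds of about 14 days or longer

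*Combined protocol and SAP*

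**What the plan says.** All references are to the combined protocol and SAP.

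- **Section 5.6.3** sets a general limit: "Treatment with itacitinib may be delayed up to 14 days to allow for resolution of toxicity". It then foresees a later restart: "The investigator should contact the sponsor medical monitor to discuss cases where treatment has been delayed for more than 14 days before restarting treatment". It also asks for weekly evaluation during a hold and describes Tables 3 and 4 as guidelines subject to clinical judgment.
- **Section 5.6.5** lists as unacceptable toxicity, requiring a permanent stop, a "Persistent AE requiring a delay of therapy for more than 14 days, unless a greater delay has been approved by the sponsor". On scope it says: "The occurrence of unacceptable toxicity not caused by the underlying disease or malignancy will be presumed to be related to study drug treatment". Section 5.7.1 makes withdrawal for unacceptable toxicity mandatory.
- **Table 3, bilirubin.** In the > 5.0-10.0 × ULN row, the instruction when resolution takes more than 14 is: "days, resume at reduced dose". No sponsor approval is mentioned. The 3.0-5.0 × ULN row keeps the reduced dose in the same situation. The > 10.0 × ULN row says to discontinue, and the AST/ALT row requires sponsor approval for exceptions.
- **Table 3, treatment-related ANC and platelets.** Both rows allow a hold of at most 14 days. The ANC row resumes "at a reduced dose if ANC count is" at least 0.5 × 10^9/L for more than 7 days. The platelet row resumes "at a reduced dose if platelet count returns spontaneously (without transfusion support) to" at least 20 × 10^9/L for more than 7 days, or to within 75% of baseline.
- **Section 5.6.2 (DLT).** An attributable platelet count below 10 × 10^9/L is a DLT if it has not recovered to at least 20 × 10^9/L after 2 weeks. Grade 4 neutropenia lasting more than 7 days is a DLT. The last criterion is "Any toxicity that can be reasonably attributed to study treatment and leading to treatment discontinuation for more than 2 weeks". Events count through Day 28, and those with a clear alternative explanation are exempt.
- **Sections 4.1 and 9.8.** More than 3 subjects with a DLT among the first 10 evaluable in a cohort terminates the study.

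**The concern.** Each passage can be followed on its own, but together they do not give one outcome for a hold that reaches or passes 14 days. A child in the > 5.0-10.0 × ULN bilirubin row may be restarted under Table 3, restarted after a conversation under 5.6.3, or permanently stopped under 5.6.5 unless approval was obtained. In the ANC and platelet rows, a late recovery leaves the site with a cap it must not exceed and a restart condition it cannot yet meet.

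The statistical stake is the platelet row. There, the wait to confirm recovery can by itself carry a child over the 2-week mark in the last DLT criterion. The DLT definition does not say whether an interruption counts as *discontinuation*. Elsewhere the protocol distinguishes the two: Table 3 uses separate instructions to interrupt and to discontinue. The resulting count drives a rule that ends the whole study.

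**Working it through.** The plan states no operating characteristic for the DLT rule, so there is no figure of that kind to reproduce. The one related figure, 75% of 28 days = 21 days for evaluability, is correct (0.75 × 28 = 21), so at most 28 − 21 = 7 days may be missed.

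**1. Day count for the ANC and platelet rows.** Let the hold start on day 0 and let r be the day from which the count stays at or above threshold. Earliest restart is r + w, where w is the confirmation period of more than 7 days. Read as full days, w = 8; read as just over 7 days, w is marginally above 7.

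| r | restart, just over 7 days | restart, w = 8 | within 14 days? |
|---|---|---|---|
| 3 | just after 10 | 11 | yes |
| 6 | just after 13 | 14 | yes |
| 7 | just after 14 | 15 | no, or at the edge |
| 8 | just after 15 | 16 | no |
| 14 | just after 21 | 22 | no |

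The cap and the restart condition collide for recovery from about day 7 onward.

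**2. ANC.** The collision requires ANC below 0.5 × 10^9/L for about 7 days or more. If that level is Grade 4 (assumed; the grading cut-off is not in the documents), more than 7 days of it is already a DLT. The hold adds a DLT only at the day-7 edge.

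**3. Platelets below 10 × 10^9/L, attributable.** Recovery on days 7-14 falls inside the 2 weeks of the platelet criterion, so that criterion is not met. Following Table 3 gives about 7 + 8 = 15 to 14 + 8 = 22 days off drug, which exceeds 2 weeks. Three conditions limit this:
- The hold must start by about Day 14, since Days 14 to 28 are 15 days.
- The 75%-of-baseline route must not apply first. If it means at least 75% of baseline, a child with baseline up to 20/0.75 = 26.7 × 10^9/L meets it on reaching 20. A higher baseline needs a count above 20.
- *Discontinuation* must include a temporary hold.

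**4. Status if it is not a DLT.** A hold of 15 days or more inside the surveillance period leaves at most 28 − 15 = 13 treated days, below 21. The child is then nonevaluable and may be replaced. The disputed choice is therefore DLT versus replaced.

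**5. Effect on the termination rule.** Take one disputed child in a cohort and an independent DLT probability p for every other child (assumed; the documents give no rate).
- Replaced: P(X ≥ 4), X ~ Binomial(10, p).
- Counted as a DLT: P(Y ≥ 3), Y ~ Binomial(9, p).

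At p = 0.10: 1 − (0.3487 + 0.3874 + 0.1937 + 0.0574) = 0.013, against 1 − (0.3874 + 0.3874 + 0.1722) = 0.053.

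| p | replaced | counted as DLT |
|---|---|---|
| 0.10 | 1.3% | 5.3% |
| 0.20 | 12.1% | 26.2% |
| 0.30 | 35.0% | 53.7% |

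**The case against.** The strongest reply is that the DLT criteria are alternatives. A child who passes the platelet criterion and meets the last one is simply a DLT, and if *discontinuation* covers interruptions, a child restarted on day 16 and one permanently stopped both count. This stands. A reader might infer that the terminating count depends on whether a site follows Table 3 or 5.6.5, and the documents do not support that in general. The bilirubin conflict, in particular, does not by itself change the count. The count becomes uncertain only if *discontinuation* may mean permanent stopping, or if a site restarts by day 14 with the platelet condition unmet.

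Other limits also stand:
- A reader might infer that the ANC and platelet rows force holds beyond 14 days. They cap the hold; the gap is that an unmet restart condition has no stated consequence.
- A reader might infer from the weekly evaluations that the limit can never be met. Table 3 also provides for monitoring as clinically indicated, and section 6.6 allows unscheduled visits, so an early recovery can be documented in time.
- The sponsor exception in 5.6.5 and the contact step in 5.6.3 can be read together, although discussion is not approval. Section 5.6.5 also concerns a persistent AE, and whether a recovered count awaiting confirmation is one is not stated.
- The 3.0-5.0 × ULN bilirubin row starts with a dose reduction, so its 14 days need not be time off drug.
- The adult study's permanent stops for thrombocytopenia (4 of 29) and low neutrophils (2 of 29) might look like a frequency for these holds. They are pooled over two doses and both disease settings, with no 28-day limit, and do not measure it.
- Continual review by the study team, investigator calls and the DMC reduce divergence between sites.

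The guideline status of Table 3 does not remove the conflict, because the stop in 5.6.5 and the withdrawal in 5.7.1 are mandatory.

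**Conclusion.** The concern holds in limited form. The passages conflict on whether a hold beyond 14 days leads to a restart or a permanent stop, most clearly for bilirubin > 5.0-10.0 × ULN. The treatment-related ANC and platelet rows contain a cap and a restart condition that recovery from about day 7 cannot jointly meet. For attributable platelets below 10 × 10^9/L, the confirmation wait can turn a recovery judged timely by one DLT criterion into a DLT under another, subject to the three conditions shown. ANC adds almost no DLTs.

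How many children this would affect cannot be derived from the documents. The size given is per disputed child: 1.3% to 5.3% at an assumed DLT rate of 10%, and 12.1% to 26.2% at 20%. It illustrates how sensitive a boundary at 4 of 10 is to one classification and does not forecast the chance of termination.

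**What to change.** At the next amendment:

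1. Reconcile Table 3, 5.6.3, 5.6.5 and the last DLT criterion (5.6.2 and the synopsis) so that each hold has one outcome. This includes whether passing 14 days calls for discussion, approval or stopping in each row, and what follows when the restart condition is unmet at day 14.
2. Define *discontinuation* in the last DLT criterion. State whether a temporary interruption counts, and whether days spent only confirming a recovered count do.
3. State the DLT and evaluability status of a hold beyond 14 days, including one approved by the sponsor.
4. Optionally, show the DMC the DLT count with and without events that qualify only through the last criterion.

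The clinical limits themselves are for the sponsor's clinicians; nothing here favours one.

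The cost is wording in four places and, if wanted, one line in a DMC table, with no extra subjects or procedures. Some events may be classified differently once the term is defined, so it is best settled before a cohort's 10-subject review.

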### **5.6.6. Criteria and Procedures for Dose Interruptions or Modifications of Corticosteroids**

Modifications to the dose of corticosteroids should be made at the treating investigator's discretion.

## **5.7. Withdrawal of Subjects From Study Treatment**

The decision to discontinue study treatment will not constitute study completion (see [Section 5.7.3](#)). In the event that the decision is made to discontinue study treatment, the treatment period will be considered complete, and the follow-up period will begin.

### **5.7.1. Withdrawal Criteria**

Subjects **must** be withdrawn from study treatment for the following reasons:

- The subject has experienced an unacceptable toxicity.
- Relapse of underlying malignancy or disorder.
- The subject is unable to tolerate itacitinib at a reduced dose specified for cohort.
- GVHD progression or lack of response. Requirement for additional systemic therapy, including corticosteroid doses greater than those used on Study Day 1, will qualify for GVHD progression.
- Further participation would be injurious to the subject's health or well-being, in the investigator's medical judgment.
- The subject becomes pregnant (may be applicable for Cohort 1).
- Consent is withdrawn.

- The study is terminated by the sponsor.
- The study is terminated by the local health authority, IRB, or IEC.

A subject **may** be withdrawn from study treatment as follows:

- If, during the course of the study, a subject is found not to have met eligibility criteria, then the medical monitor, in collaboration with the investigator, will determine whether the subject should be withdrawn from the study.
- If a subject is noncompliant with study procedures or study drug administration in the investigator's opinion, the sponsor should be consulted for instruction on handling the subject.

### **5.7.2. Withdrawal Procedures**

In the event that the decision is made to permanently discontinue the study drug, the subject will be withdrawn from the study and the EOT visit should be conducted. Reasonable efforts should be made to have the subject return for a follow-up visit as described in Section [6.5](#). The last date of the last dose of study drug and the reason for subject withdrawal will be recorded in the eCRF.

**If a subject is withdrawn from study treatment:**

- The study monitor or sponsor must be notified.
- The reason(s) for withdrawal must be documented in the subject's medical record and in the eCRF.
- The EOT visit should be performed.
- The date of the EOT visit should be registered in the IRT.
- Subjects must be followed for safety until the time of the follow-up visit or until study drug-related toxicities resolve, return to baseline, or are deemed irreversible, whichever is longest.

If the subject discontinues study treatment and actively withdraws consent for collection of follow-up data (safety follow-up or disease assessment), then no additional data collection should occur; however, subjects will have the option of withdrawing consent for study treatment but continuing in the follow-up period of the study for safety/efficacy assessments.

### **5.7.3. Study Completion**

A subject will be considered as completing the study if they meet any of the following criteria:

- Subject dies and a date of death is available.
- Subject is known to have died; however, the date of death cannot be obtained.  
(*Note:* Every effort must be made to obtain the date of death.)
- Subject has discontinued study treatment and has withdrawn consent for collection of follow-up for new GVHD therapy and survival status.

## 5.7.4. Concomitant Medications

### 5.7.4.1. Permitted Medications

Concomitant treatments and/or procedures that are required to manage a subject's medical condition (including prophylactic and/or supportive care medications as described in Section 5.4) during the study will also be recorded in the eCRF.

## 5.7.5. Restricted Medications

The following medications have restrictions on use during the treatment period of the study:

- Aspirin.
- Coadministration with the following potent CYP3A inhibitors: itraconazole, voriconazole, mibepradil, and clarithromycin. If the subject's medical condition requires treatment with any of these drugs, dose reduction of itacitinib is recommended as follows (see rationale in Section 1.5):
  - In children 12 years of age and older, doses should be reduced to 100 mg QD.
  - In children 6 to < 11 years old, doses should be reduced to 50 mg QD.
  - In children 2 to < 6 years old, doses should be reduced to 25 mg QD.
  - In children > 8 kg but < 2 years old, doses should be reduced to 17.5 mg QD.
  - In children  $\leq$  8 kg but  $\geq$  28 days old, doses should be reduced to 0.7 mg/kg QD.

The coadministration with those medications should be avoided during the 28-day surveillance period in subjects enrolled in Part 1 of the study. The sponsor's medical monitor may be consulted for advice when using these agents. No dose adjustment is recommended for concomitant administration of other CYP3A4 inhibitors.

- Coadministration with potent CYP3A4 inducers.
- If concomitant administration of an anticoagulant/antiplatelet medication is indicated, then caution and enhanced monitoring is required. History of thrombocytopenia should be a factor in the choice of anticoagulant and dose.

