In a Phase 1 study in aGVHD subjects (INCB 39110-108), treatment interruptions and stepwise 100 mg dose reductions were used to manage toxicity. In an analysis of the data, efficacy was not affected in subjects who demonstrated Day 28 response and had a dose reduction for any reason. Dose reductions also facilitated platelet recovery in subjects with platelet count decreases receiving treatment, although recovery was also observed in subjects who did not have a dose reduction. Thus, the proposed itacitinib tapering schedule is not expected to negatively affect efficacy in responding subjects, and clinicians are permitted to re-escalate the dose of itacitinib in subjects who initiate a taper but subsequently begin to demonstrate signs or symptoms of GVHD progression.

Observed data from Study INCB 39110-108 demonstrated that there is an approximate 2-fold increase in exposure when itacitinib is coadministered with posaconazole. Given the risk/benefit profile observed in Study INCB 39110-108, no dose adjustment is recommended with coadministration of posaconazole. In a healthy volunteer study, coadministration of itacitinib 200 mg with itraconazole 200 mg QD resulted in a nearly 5-fold increase in exposure of itacitinib. Posaconazole is a less potent CYP3A4 inhibitor than itraconazole based on fold increase in midazolam exposure with coadministration, 6.23 compared with 10.8 ([University of Washington School of Pharmacy 2002](#)), which could explain the difference in exposure change between coadministration of itacitinib with posaconazole or itraconazole. However, taking into consideration the result of the healthy volunteer drug interaction study with itraconazole and given the lack of information regarding the risk/benefit profile in patients receiving strong CYP3A4 inhibitors more potent than posaconazole, subjects taking the following potent CYP3A4 inhibitors should have a dose reduction of itacitinib to half of the initial dose (eg, from 200 mg to 100 mg QD): itraconazole, voriconazole, mibefradil, and clarithromycin. No dose adjustment is recommended for concomitant administration of other CYP3A4 inhibitors.

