#### **3.1. Subject Inclusion Criteria**

A subject who meets all of the following criteria may be included in the study:

1. Male and female subjects:
  - a. 12 to < 18 years old (Cohort 1)
  - b. 6 to < 12 years old (Cohort 2)
  - c. 2 to < 6 years old (Cohort 3)
  - d. Weighing > 8 kg to < 2 years old (Cohort 4)
  - e. 28 days old to weighing  $\leq$  8 kg (Cohort 5)
2. Undergone 1 allo-HSCT from any donor HLA type (related or unrelated donor with any degree of HLA matching) using any graft source (bone marrow, peripheral blood stem cells, or cord blood). Recipients of myeloablative and reduced-intensity conditioning regimens are eligible.
3. Clinically suspected Grade II to IV aGVHD as per MAGIC criteria, occurring after allo-HSCT and any GVHD prophylactic medication. Efforts should be made to obtain biopsies to pathologically confirm aGVHD. In cases where a biopsy is negative, unable to be obtained, or clinically contraindicated, clinical suspicion of aGVHD by the treating physician is sufficient, provided that alternative diagnoses of drug effects or infection are adequately ruled out.
4. Evidence of myeloid engraftment (eg, ANC  $\geq 0.5 \times 10^9/L$  for 3 consecutive assessments if ablative therapy was previously used). Use of growth factor supplementation is allowed.
5. GFR  $> 50 \text{ mL/min}/1.73 \text{ m}^2$  as estimated using modified Schwartz formula ([Schwartz et al 2009; Appendix D](#)).
6. May be applicable to Cohort 1: be willing to avoid pregnancy or fathering children based on 1 of the following criteria:
  - a. Females of nonchildbearing potential (ie, surgically sterile with a hysterectomy and/or bilateral oophorectomy OR  $\geq 12$  months of primary amenorrhea).
  - b. Females of childbearing potential who have a negative serum pregnancy test at screening and who agrees to take appropriate precautions to avoid pregnancy (with at least 99% certainty) from screening through safety follow-up. Permitted methods that are at least 99% effective in preventing pregnancy (see [Appendix C](#)) should be communicated to the subject and her understanding confirmed.
  - c. Males of fathering potential who agree to take appropriate precautions to avoid fathering children (with at least 99% certainty) from screening through safety follow-up. A male is considered fertile after puberty unless permanently sterile by bilateral orchiectomy. Permitted methods that are at least 99% effective in preventing

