#### **5.2.1. Description and Administration**

Itacitinib 100 mg (free base equivalent) sustained-release tablets are oval-shaped and purple and are debossed with "INCY" on one side and "100" on the other side. Tablets contain the active ingredient, hypromellose, microcrystalline cellulose, lactose monohydrate, and magnesium stearate and are coated with a nonfunctional film coating.

Itacitinib 25 mg (free base equivalent) sustained-release tablets are uncoated round tablets with no debossing. Tablets contain the active ingredient, hypromellose, microcrystalline cellulose, lactose monohydrate, and magnesium stearate.

Two additional age-appropriate formulations are being developed that could be used for Cohorts 2, 3, 4, and/or 5.

The currently recommended doses are outlined as follows. They are based on simulation and include assumptions regarding the relationship between age/weight and clearance and relative bioavailability of the yet-to-be-developed age-appropriate formulations. As data become available regarding these assumptions, dosing recommendations may change.

- 12 to < 18 years old (Cohort 1): Subjects will receive oral itacitinib at a dose level of 200 mg QD (2 × 100 mg tablets).
- 6 to < 12 years old (Cohort 2): Subjects will receive oral itacitinib at a dose level of 100 mg QD (1 × 100 mg tablet or first age-appropriate formulation).
- 2 to < 6 years old (Cohort 3): Subjects will receive oral itacitinib at a dose level of 50 mg QD (first age-appropriate formulation) or 2 × 25 mg tablets.
- Weighing > 8 kg to < 2 years old (Cohort 4): Subjects will receive oral itacitinib at a dose level of 35 mg QD (first age-appropriate formulation).
- 28 days old to weighing ≤ 8 kg (Cohort 5): Subjects will receive oral itacitinib at a dose level of 1.4 mg/kg QD (second age-appropriate formulation).

Subjects may have dose reductions or modifications of itacitinib during the course of treatment based on AEs, clinical evaluation, and laboratory assessments. See Section 5.6 for dose modifications of study drug.

Subjects are permitted to remain on itacitinib treatment until withdrawal from study treatment is considered necessary as per Section 5.7.

In case the PK/PD analyses described in Section 9.6 recommend a dose increase/decrease for the study cohort and subsequent age-specific cohorts, the changes will be implemented only after approval of a substantial amendment by the Competent Authorities.

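### The reduced-dose list for potent CYP3A inhibitors in Section 5.7.5 has no entry for 11-year-olds, who belong to Cohort 2

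*Combined protocol and SAP*

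**What the plan says.** Section 5.7.5 (Restricted Medications) names itraconazole, voriconazole, mibefradil and clarithromycin as potent CYP3A inhibitors and recommends a reduced itacitinib dose for each age or weight group. The two entries that matter here are "In children 12 years of age and older, doses should be reduced to 100 mg QD" and "In children 6 to < 11 years old, doses should be reduced to 50 mg QD".

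The cohort boundaries differ from that list. Section 5.2.1 sets the starting dose as "6 to < 12 years old (Cohort 2): Subjects will receive oral itacitinib at a dose level of 100 mg QD". The same range of 6 to under 12 years appears in the synopsis and in Sections 3.1, 4.1 and 9.2.

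Section 5.7.5 refers to Section 1.5 for its rationale. Section 1.5 says that subjects on these inhibitors "should have a dose reduction of itacitinib to half of the initial dose", with no age limit. Administrative Change 1 (28 OCT 2019) adds ketoconazole under both sections and repeats the half-dose recommendation. It does not touch the age bands.

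For the run-in, Section 5.7.5 adds: "The coadministration with those medications should be avoided during the 28-day surveillance period in subjects enrolled in Part 1 of the study".

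**The concern.** The upper limit of the Cohort 2 entry is 11 years where the cohort's own limit is 12. A child between the 11th and 12th birthdays is eligible, starts on 100 mg QD, and has no line in the list that a site would use to set the reduced dose. A site that finds no line might make no reduction. If it borrowed the adjacent line for older children, the result would be 100 mg QD, which for Cohort 2 is the full dose.

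What is at stake is mainly the safety of the individual child. Section 1.5 reports that itraconazole in healthy volunteers "resulted in a nearly 5-fold increase in exposure of itacitinib", and says that risk/benefit information is lacking for inhibitors more potent than posaconazole. Section 5.6.3 notes that subjects may enter with compromised marrow function, and Section 1.5 names myelosuppression and infection as risks. Section 5.4 allows anti-infective prophylaxis to continue, so use of a listed antifungal is foreseeable. The avoidance instruction covers only the 28-day surveillance period of the run-in. It does not cover later treatment or children who enter in Phase 2.

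**Working it through.** **Step 1. Reproduce the listed doses.** Starting doses are from Section 5.2.1 and reduced doses from Section 5.7.5.

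| Cohort | Age or weight in 5.2.1 | Start (QD) | Group in 5.7.5 | Reduced (QD) | Ratio |
|---|---|---|---|---|---|
| 1 | 12 to < 18 y | 200 mg | 12 y and over | 100 mg | 100/200 = 0.5 |
| 2 | 6 to < 12 y | 100 mg | 6 to < 11 y | 50 mg | 50/100 = 0.5 |
| 3 | 2 to < 6 y | 50 mg | 2 to < 6 y | 25 mg | 25/50 = 0.5 |
| 4 | > 8 kg, < 2 y | 35 mg | > 8 kg, < 2 y | 17.5 mg | 17.5/35 = 0.5 |
| 5 | 28 days and over, ≤ 8 kg | 1.4 mg/kg | 28 days and over, ≤ 8 kg | 0.7 mg/kg | 0.7/1.4 = 0.5 |

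Every listed dose is half the cohort's starting dose, as Section 1.5 says it should be. The doses are right; only one age limit is out of line.

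**Step 2. Check coverage by age.** The age intervals in Section 5.7.5 are [2, 6), [6, 11) and [12, 18). Checked against each whole year from 2 to 17, they leave out one year: 11. With [6, 12) in place of [6, 11), none is left out.

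**Step 3. Dose implied for an 11-year-old.** 0.5 × 100 mg = 50 mg QD. A child left unreduced would receive 100/50 = 2 times that dose.

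**Step 4. Exposure with itraconazole.** This assumes that the healthy-volunteer ratio (rounded to 5) applies to children and that exposure is proportional to dose. Exposure is relative to 100 mg QD without an inhibitor.

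- Unreduced: 100 × 5 / 100 = 5.0
- Halved: 50 × 5 / 100 = 2.5

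For comparison, Section 1.5 reports that "there is an approximate 2-fold increase in exposure when itacitinib is coadministered with posaconazole" and recommends no dose change for that drug.

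**Step 5. How many children.** The documents give neither the age distribution within Cohort 2 nor the rate of inhibitor use. Assume an even age spread, so that 1 of 6 year-bands is in the gap, and inhibitor use of 10% to 50%.

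- Full cohort: 30 × 1/6 = 5 eleven-year-olds; 5 × 0.10 to 5 × 0.50 = 0.5 to 2.5 children
- First 10 evaluable: 10 × 1/6 = 1.67; × 0.10 to 0.50 = 0.17 to 0.83 children, before the avoidance instruction is applied

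These figures count children for whom the list has no line, not children given the wrong dose.

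**The case against.** The strongest reply is that the correct dose is settled elsewhere. Section 1.5 gives a half-dose rule for all ages, and the list in Section 5.7.5 points to it. Table 4 allows only one reduction, to 50%. Administrative Change 1, which is later text and expressly covers Section 5.7.5, restates the rule without age bands. The medical monitor may be consulted, and the reductions are worded as recommendations. Borrowing the line for older children is also an unlikely mistake: it would mean applying that line to a child who is not yet 12, and reducing 100 mg to 100 mg.

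Most of this stands. A careful reader reaches 50 mg QD, and the misreading upward is improbable. The more plausible failure is a site that finds no line for its patient and looks no further. The cross-reference and the medical monitor make that less likely but do not rule it out.

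It is also fair to say that the 5-fold figure is for itraconazole only. The documents give no ratio for the other listed inhibitors, so the comparison of 5 with 2.5 cannot be carried over to them. The inhibitor-use range has no source in the documents, and the share of sites that would miss the general rule cannot be estimated from them.

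**Conclusion.** The point holds. The current text of Section 5.7.5 leaves exactly one year of age in Cohort 2 without a reduced dose, in a paediatric dosing list that sites will use directly. The documents support a single correction, 50 mg QD.

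The consequence is small in number and confined to individual safety: at most a twofold dosing error per affected child, with about 0.5 to 2.5 of 30 Cohort 2 children in the gap under the assumptions in Step 5. The effect on run-in DLT and AUC data is slight, because the listed inhibitors should be avoided in those 28 days. ORR at Day 28, the sample size, the DLT rule and the analyses are unchanged. It should be corrected because a dose for a child should not have to be inferred from a background section.

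**What to change.** In Section 5.7.5, change the upper age limit of the 50 mg QD entry from under 11 to under 12 years, so that it matches Cohort 2 in Sections 3.1 and 5.2.1. Tell sites at the same time.

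The cost is one number and one notice. Administrative Change 1 is a precedent: it changed this same section by letter, to be incorporated when an amendment is next required. No analysis, data collection or visit is affected.
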